12. DATA AND SAFETY MONITORING

12.1 SAFETY MONITORING

12.1.1 Principal Investigator

Accrual and safety data and conduct of the trial will be monitored by the PI and research team on an ongoing basis. The protocol will be continuously evaluated for any unusual or unpredicted complications with the aim of detecting and preventing unacceptable increase in morbidity and mortality over and above that anticipated from standard allogeneic stem cell transplants. (See stopping rules in section 11.3.4). Given that safety was established in the prior Phase 1 study, non-serious adverse events will not be collected (see definition Section 12.2).

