8.2 IMMEDIATE TRANSFUSION REACTION

Administration of BMSC will be performed according to NIH Clinical Center standard operating procedure: [Administration of Products of Cellular Therapy](#). If an allergic or other acute reaction occurs, studies appropriate for investigation of a transfusion reaction will be performed (urinalysis, CBC, Coomb's test). Any adverse reactions should prompt interruption of the infusion and should be reported to the principal investigator.

No further BMSC infusions will be administered to a subject in the event of:

- recurrent infusion related toxicity *despite premedication* (moderate toxicity is defined as requiring interruption or discontinuation of BMSC administration, which is not rapidly responsive to symptomatic medication)
- any CTCAE v4.0 grade 4 acute infusion reaction (defined as requiring discontinuation of infusion AND urgent cardiopulmonary intervention) or grade 4 hypersensitivity reaction (anaphylaxis) at least possibly related to BMSC infusions
- any CTCAE v4.0 grade 3 infusion reaction that does not resolve completely within 2 hours
- any CTCAE v4.0 grade 3 acute infusion reaction or hypersensitivity that recurs when the infusion is restarted.

*Abbreviated Title: Early BMSC Pilot for Acute GVHD**Version Date: 6/16/2016*

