11.3 STATISTICAL ANALYSIS

11.3.1 Methods of Statistical Analysis

The planned analyses will include descriptive statistics on response rates, biomarkers, and the incidence and severity of adverse events. The proportions of treatment related adverse events and their severity will be estimated using the sample proportions, and their inferences including confidence intervals and hypotheses testing will be evaluated using Binomial distributions. The time to adverse events will be analyzed using appropriate tools in survival analysis such as Kaplan-Meier estimates. Graphical tools will be used to display the appropriate estimates.

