12.2.2 Adverse Event Management

The following adverse event management guidelines are intended to ensure the safety of each subject while on the study. The descriptions and grading scales found in the revised NCI Common Terminology Criteria for Adverse Events (CTCAE) version 4.0 will be utilized for AE reporting. All appropriate treatment areas should have access to a copy of the CTCAE version 4.0. A copy of the CTCAE version 4.0 can be downloaded from the [CTEP website](#).

Attribution

Relationship	Attribution	Description
Unrelated to investigational agent/intervention ¹	Unrelated	The AE is clearly NOT related to the intervention
	Unlikely	The AE is doubtfully related to the intervention
Related to investigational agent/intervention ¹	Possibly	The AE may be related to the intervention
	Probably	The AE is likely related to the intervention
	Definitely	The AE is clearly related to the intervention

¹**NOTE:** AEs listed as ‘possibly, probably, or definitely’ related to the investigational agent/intervention are considered to have a suspected ‘reasonable causal relationship’ to the investigational agent/intervention (ICH E2A).

The following are expected outcomes for the transplant recipient (not necessarily as a result of this study) and will be documented in the subject’s medical record but not reported to IRB unless they meet the criteria for an SAE or UP:

- Renal insufficiency
- Hepatic insufficiency
- Transient cardiac arrhythmias
- Transient cardiac insufficiency
- Pulmonary insufficiency
- Neutropenia and its complications
- Thrombocytopenia and its complications
- Anemia and its complications
- Transfusion reactions
- Treatable infections from bacteria, viruses, protozoa and fungi
- Late effects of transplant regimens including: chronic fatigue, cataracts, infertility, growth impairment, hypothyroidism, bone complications, and dental caries
- Headache, insomnia, psychosis, mood changes, disorientation, seizures from metabolic imbalance
- Nausea, vomiting, diarrhea, mucositis, weight loss, dry mouth, hiccoughs, constipation
- Well-characterized drug reactions - allergic manifestations, "red man" syndrome, steroid effects
- Well-characterized drug side effects from drugs used routinely in transplant recipients (e.g.; preparative regimen chemotherapy, immunosuppressive drugs, antimicrobials)
- Common side effects of antiemetics, analgesics, anti-inflammatory agent and known complications of steroid therapy

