Abbreviated Title: Early BMSC Pilot for Acute GVHD

Version Date: 6/16/2016

- Complications from intravenous catheters, thrombotic occlusion, infection, local reactions, cardiac arrhythmia
- Expected adverse events related to investigational reagents and transplant drugs are listed in section 13.3.

The following are expected transplant outcomes that will be reported in summary form at the time of continuing review but will not be reported to IRB at each occurrence unless they meet the criteria of an SAE or UP:

- Acute graft-versus-host disease
- Chronic graft-versus-host disease
- Graft failure / graft rejection
- Venocclusive disease
- Hemorrhagic cystitis
- Cytomegalovirus reactivation or disease
- Autoimmune phenomena
- EBV reactivation or disease
- Fungal infections
- Disease relapse or progression

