12.5 DSMB REPORTING

Any UP observed during the clinical trial and for which there is a relationship with the use of BMSC cells and the conduct of the study will be reported within 24 hours to the Data and Safety Monitoring Board (DSMB). A summary of all SAEs and AEs will be included for review at the regularly scheduled DSMB meeting.

12.5.1 Serious Adverse Event Reporting on Cell Therapy Products to the NHLBI IRB and FDA

If a cell product deviation (or any component thereof) occurs during or after its manufacture, a report of the event, and information relevant to the event, associated with the manufacturing will be submitted to the NHLBI IRB and the FDA by the PI and/or IND sponsor, in collaboration with CPS/DTM, to include testing, processing, packing, labeling, or storage, or holding or distribution of the product, if the event meets the following criteria:

- (i) Represents a deviation from current good manufacturing practice, applicable regulations, applicable standards, or established specifications that may affect the safety, purity, or potency of that product; or
- (ii) Represents an unexpected or unforeseeable event that may affect the safety, purity, or potency of that product;

Cell product deviations will be reported as soon as possible but at a date not to exceed 45-calendar days from the date the PI/research team or CPS, DTM acquired information reasonably suggesting that a reportable event has occurred.

FDA reporting: All HCT/P deviations involving 361 cell products will be reported using [MedWatch Form FDA 3500A](#) according to FDA publication “Guidance for Industry: MedWatch Form FDA 3500A: Mandatory Reporting of Adverse Reactions Related to Human Cells, Tissues, and Cellular and Tissue-Based Products (HCT/Ps).

12.5.2 Action Plan for Positive Results on Cell Product Safety Testing:

In the unlikely event that a positive sterility test or mycoplasma test result is obtained after distribution of the BMSC product, or after administration of the product to the subject, the following steps will be initiated IMMEDIATELY:

- a) CPS, DTM personnel will notify the principal investigator, [name] [contact]) (and [name]) or through the page operator. As soon as the identification and sensitivity report from positive sterility is available, a copy of the final report will be sent to the PI. The DTM QS officer and CPS Supervisor will determine the need for quality improvement based on the nature and extent of the incident.

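### Section 12.1.1 leaves non-serious adverse events uncollected, but Section 12.5 promises the DSMB a summary of them; if 12.1.1 is followed, the safety tables give no overall or non-serious infusion-reaction rate.

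*Combined protocol and SAP*

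**What the plan says.** Section 12.1.1 sets the collection rule: "Given that safety was established in the prior Phase 1 study, non-serious adverse events will not be collected". Section 12.5 sets the reporting rule: "A summary of all SAEs and AEs will be included for review at the regularly scheduled DSMB meeting".

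Section 11.3.1 describes the analyses without limiting them to serious events. Its general statement is: "The planned analyses will include descriptive statistics on response rates, biomarkers, and the incidence and severity of adverse events". It then turns to estimation for events attributed to treatment: "The proportions of treatment related adverse events and their severity will be estimated using the sample proportions". Event times are covered as well: "The time to adverse events will be analyzed using appropriate tools in survival analysis such as Kaplan-Meier estimates".

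Three other places assume that AEs are captured:

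- Section 10.1 lists adverse events among the data entered directly on CRFs, and adds that data will be abstracted from progress notes.
- Section 11.2 has subjects with BMSC-related adverse events followed until the toxicity resolves or stabilizes. It does not restrict this to serious events.
- The Appendix 3 calendar has an adverse-events row running from Day 0.

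Infusion reactions also have a clinical route. Section 8.2 says: "Any adverse reactions should prompt interruption of the infusion and should be reported to the principal investigator". Section 12.2.2 lists expected events, transfusion reactions among them, that go into the "medical record but not reported to IRB unless they meet the criteria for an SAE or UP". The same list includes this entry: "Expected adverse events related to investigational reagents and transplant drugs are listed in section 13.3".

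**The concern.** Safety is part of the primary objective (Section 1.1.1), yet the statistician and the DSMB cannot tell whether the promised AE outputs cover all AEs or SAEs only. Site staff cannot follow both 12.1.1 and 12.5.

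The events at issue are the ones most expected from this product. Section 13.3.1 describes infusion side effects as minor: fever, hives, nasal congestion. The meta-analysis cited in Section 2.6 found transient fever to be the only significant association with BMSC. Events of this kind would usually fall short of the SAE definition in Section 12.2.1.

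Under 12.1.1 they would mostly be absent from the safety tables, in a trial that gives several times as many infusions per subject as phase I did. The reason offered for not collecting them is a 10-subject study.

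**Working it through.** **1. The plan's own figure.** Section 11.3.2 gives n = 23, a null rate of 75%, an alternative of 95% and one-sided alpha of 0.05. Section 11.3.4.2 gives the rule: at least 21 of 23 subjects without a TRSAE.

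- Power = P(X ≥ 21 | n = 23, p = 0.95) = 0.95^23 + 23 × 0.95^22 × 0.05 + 253 × 0.95^21 × 0.05^2 = 0.3074 + 0.3721 + 0.2154 = 0.895.
- Size at p = 0.75: 0.049.

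The stated 89.5% reproduces. Every input concerns TRSAEs, which are serious by definition, so the collection rule for non-serious AEs changes nothing here.

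**2. The passages side by side.**

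| Section | What it requires | Compatible with SAE-only collection? |
|---|---|---|
| 12.1.1 | No collection of non-serious AEs | This is the SAE-only rule |
| 12.5 | DSMB summary naming SAEs and AEs separately | No |
| 11.3.1 | AE incidence, severity, treatment-related proportions, time to event | Only if read as covering SAEs alone, which it does not say |
| 10.1 | AEs on CRFs; abstraction from progress notes | Only if read as covering SAEs alone |
| 11.2 | BMSC-related AEs followed to resolution or stabilization | Only if read as covering SAEs alone |
| Appendix 3 | Adverse-events row | Only if read as covering SAEs alone |

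The conflict with 12.5 is direct. The others conflict on their ordinary wording.

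**3. What phase I shows.** Section 2.6.1 reports one infusion reaction, a grade 1 pruritus; Section 2.5.1 gives 10 subjects and three weekly doses.

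- Rate: 1/10 = 10%, exact (Clopper-Pearson) 95% CI 0.3% to 44.5%.
- TRSAEs: 0/10, one-sided 95% upper limit 1 − 0.05^(1/10) = 25.9%.

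**4. Exposure planned here.** Section 3.4.1 plans 8 infusions, or 12 without a complete response: 23 × 8 = 184 to 23 × 12 = 276 infusions, before permitted misses and early stops. Phase I planned 10 × 3 = 30.

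**5. Likely number of affected subjects.** The documents give no non-serious infusion-reaction rate for this schedule, so a range is assumed.

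| Assumed per-subject rate | Expected of 23 | Chance of at least one, 1 − (1 − p)^23 |
|---|---|---|
| 5% | 23 × 0.05 = 1.15 | 69% |
| 10% | 23 × 0.10 = 2.3 | 91% |
| 20% | 23 × 0.20 = 4.6 | 99% |

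**6. What recording them would give.** Two affected subjects would give 2/23 = 8.7% (exact 95% CI 1.1% to 28.0%). None would give a one-sided 95% upper limit of 1 − 0.05^(1/23) = 12.2%. An SAE-only table yields neither statement for non-serious reactions.

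**The case against.** The best defence is that 12.1.1 is a deliberate decision with a stated reason, and that SAE-only collection is a legitimate policy in a population with many unrelated complications. SAEs are also AEs, so 11.3.1 can be read as covering whatever is collected, and its treatment-related sentence may be loose wording for TRSAEs. Nor is an infusion-reaction rate a named endpoint. This has force against the 11.3.1 part of the point. It does not rescue 12.5, which names SAEs and AEs separately. If the policy is intended, 12.5 promises something that cannot be delivered.

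Three stronger readings are tempting and should be resisted.

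- **A reader might infer that minor reactions would be lost altogether.** They would not. They go to the principal investigator (8.2), expected ones go into the medical record (12.2.2), and 10.1 plans both CRF capture of adverse events and abstraction from progress notes. However, 10.1 speaks of some source data and does not name non-serious AEs. It therefore adds to the inconsistency rather than resolving it.
- **A reader might infer that no infusion reaction of any kind would be counted.** Serious reactions remain SAEs, reactions meeting 8.2 or 9.1.1 end infusions and would be seen that way, and non-serious unanticipated problems are still reported (12.3.2). Only the overall and the non-serious rates are missing.
- **A reader might take the phase I split of 7 SAEs and 13 non-SAEs (13/20 = 65%) as the size of the loss.** Section 2.6.1 says none of these events was attributable to BMSC, and the remedy preferred here would still leave unrelated non-serious events uncollected. The text does not say whether the pruritus is among the 13. The figure therefore does not measure what the change would recover.

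**Conclusion.** The point holds: 12.1.1 contradicts 12.5, and it fits poorly with 11.3.1, 10.1, 11.2 and the Appendix 3 calendar. If 12.1.1 is followed, the AE tables and the DSMB summary are SAE-only and give no overall or non-serious infusion-reaction rate. Between about 1 and 5 of 23 subjects would have a reaction missing from the tables, if the true per-subject rate of non-serious reactions is 5% to 20%. That range is an assumption, and the phase I interval of 0.3% to 44.5% is too wide to narrow it.

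The documents do not support reading this as a threat to the primary analysis: the primary endpoint, the three-subject TRSAE stopping rule and the 89.5% power all stand. It should be corrected because safety is a primary objective and the DSMB needs to know what its summary contains.

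**What to change.** **Preferred.** Amend 12.1.1 so that infusion reactions, and non-serious AEs at least possibly related to BMSC, are recorded on the CRF and graded by CTCAE v4.0. Unrelated non-serious AEs stay uncollected. State in 11.3.1 and 12.5 that the tables and the DSMB summary cover SAEs plus this set, and bring 10.1, 11.2 and the Appendix 3 calendar into line. Report infusion reactions per subject with exact binomial intervals.

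The cost is modest extra CRF entry and attribution work over the 7 to 11 weeks of monitoring. Subjects are already monitored at each infusion and reactions already go to the principal investigator. This does change a stated collection decision, so it goes beyond editing.

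**If the sponsor keeps SAE-only collection.** Limit 11.3.1, 12.5, 10.1 and the calendar explicitly to SAEs, clarify the scope of 11.2, and state that no overall infusion-reaction rate will be reported. This costs only wording and restores consistency, but the trial then gives no estimate of how often minor reactions occur on the longer schedule.

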12.1.2 NHLBI IRB

Prior to implementation of this study, the protocol and the proposed subject consent and assent forms will be reviewed and approved by the properly constituted IRB operating according to the 45 CFR 46, 21 CFR 50 and 56. This committee must approve all amendments to the protocol or informed consent, and conduct continuing annual review so long as the protocol is open to accrual or sample and/or data analysis continues.

12.1.3 DSMB

The NHLBI Data Safety and Monitoring Board will review the protocol annually or semiannually. A progress report will be forwarded to the DSMB at this time. The DSMB may recommend early termination of the study for considerations of safety and efficacy.

12.1.4 FDA

An annual progress report, any amendments to the protocol, and any change in the status of the protocol will be forwarded to FDA.

Abbreviated Title: Early BMSC Pilot for Acute GVHD

Version Date: 6/16/2016

12.1.5 Data Integrity and Study Conduct

Regularly scheduled clinical trial monitoring will be performed by experienced contracted clinical trial monitors according to established procedures established by the Office of Clinical Affairs, NHLBI.

12.2 ADVERSE EVENTS

12.2.1 Definitions

Adverse Event (AE): Any untoward or unfavorable medical occurrence in a human subject, including any abnormal sign (e.g., abnormal physical exam or laboratory finding), symptom, or disease, temporally associated with the subject's participation in the research, whether or not considered related to the research.

An abnormal laboratory value will be considered an AE if the laboratory abnormality is characterized by any of the following:

- Results in discontinuation from the study
- Is associated with clinical signs or symptoms
- Requires treatment or any other therapeutic intervention
- Is associated with death or another serious adverse event, including hospitalization
- Is judged by the Investigator to be of significant clinical impact
- If any abnormal laboratory result is considered clinically significant, the investigator will provide details about the action taken with respect to the test drug and about the patient's outcome.

Serious Adverse Event (SAE): A serious adverse event that:

- results in death;
- is life-threatening (places the subject at immediate risk of death from the event as it occurred);
- results in in-patient hospitalization or prolongation of existing hospitalization;
- results in a persistent or significant incapacity;
- results in a congenital anomaly/birth defect; or
- based upon appropriate medical judgment, may jeopardize the subject's health and may require medical or surgical intervention to prevent one of the other outcomes listed in this definition.

Suspected adverse reaction: Suspected adverse reaction means any adverse event for which there is a reasonable possibility that the drug caused the adverse event. For the purposes of IND safety reporting, 'reasonable possibility' means there is evidence to suggest a causal relationship between the drug and the adverse event. A suspected adverse reaction implies a lesser degree of certainty about causality than adverse reaction, which means any adverse event caused by a drug.

Serious event: An event is serious if it meets the definition of a serious adverse event (above) or if it requires immediate corrective action by a PI and/or IRB to protect the safety, welfare or rights of subjects.

*Abbreviated Title: Early BMSC Pilot for Acute GVHD**Version Date: 6/16/2016*

Unexpected adverse reaction: An adverse event or suspected adverse reaction is considered “unexpected” if it is not listed in the investigator brochure or is not listed at the specificity or severity that has been observed; or, if an investigator brochure is not required or available, is not consistent with the risk information described in the general investigational plan or elsewhere in the current application. “Unexpected”, also refers to adverse events or suspected adverse reactions that are mentioned in the investigator brochure as occurring with a class of drugs or as anticipated from the pharmacological properties of the drug, but are not specifically mentioned as occurring with the particular drug under investigation.

Unanticipated Problem (UP): Any incident, experience, or outcome that meets all of the following criteria:

1. **unexpected** in terms of nature, severity, or frequency in relation to
 - a. the research risks that are described in the IRB-approved research protocol and informed consent document; Investigator’s Brochure or other study documents; and
 - b. the characteristics of the subject population being studied; and
2. **related or possibly related** to participation in the research; and
3. places subjects or others at a **greater risk of harm** (including physical, psychological, economic, or social harm) than was previously known or recognized.

Unanticipated Problem that is not an Adverse Event: An unanticipated problem that does not fit the definition of an adverse event, but which may, in the opinion of the investigator, involves risk to the subject, affect others in the research study, or significantly impact the integrity of research data. For example, report occurrences of breaches of confidentiality, accidental destruction of study records, or unaccounted-for study drug.

Protocol Deviation (PD): Any change, divergence, or departure from the IRB approved research protocol.

Non Compliance: The failure to comply with applicable NIH HRPP policies, IRB requirements, or regulatory requirements for the protection of human research. Noncompliance may be further characterized as:

1. **Serious non-compliance:** Non-compliance that:
 - a. Increases risks, or causes harm, to participants.
 - b. Decreases potential benefits to participants.
 - c. Compromises the integrity of the NIH HRPP.
 - d. Invalidates the study data.
2. **Continuing non-compliance:** Non-compliance that is recurring. An example may be a pattern of non-compliance that suggests a likelihood that, absent an intervention, non-compliance will continue. Continuing noncompliance could also include a failure to respond to IRB requests to resolve previous allegations of non-compliance.
3. **Minor (non-serious) non-compliance:** Non-compliance that, is neither serious nor continuing.

12.2.2 Adverse Event Management

The following adverse event management guidelines are intended to ensure the safety of each subject while on the study. The descriptions and grading scales found in the revised NCI Common Terminology Criteria for Adverse Events (CTCAE) version 4.0 will be utilized for AE reporting. All appropriate treatment areas should have access to a copy of the CTCAE version 4.0. A copy of the CTCAE version 4.0 can be downloaded from the [CTEP website](#).

Attribution

Relationship	Attribution	Description
Unrelated to investigational agent/intervention ¹	Unrelated	The AE is clearly NOT related to the intervention
	Unlikely	The AE is doubtfully related to the intervention
Related to investigational agent/intervention ¹	Possibly	The AE may be related to the intervention
	Probably	The AE is likely related to the intervention
	Definitely	The AE is clearly related to the intervention

¹**NOTE:** AEs listed as ‘possibly, probably, or definitely’ related to the investigational agent/intervention are considered to have a suspected ‘reasonable causal relationship’ to the investigational agent/intervention (ICH E2A).

The following are expected outcomes for the transplant recipient (not necessarily as a result of this study) and will be documented in the subject’s medical record but not reported to IRB unless they meet the criteria for an SAE or UP:

- Renal insufficiency
- Hepatic insufficiency
- Transient cardiac arrhythmias
- Transient cardiac insufficiency
- Pulmonary insufficiency
- Neutropenia and its complications
- Thrombocytopenia and its complications
- Anemia and its complications
- Transfusion reactions
- Treatable infections from bacteria, viruses, protozoa and fungi
- Late effects of transplant regimens including: chronic fatigue, cataracts, infertility, growth impairment, hypothyroidism, bone complications, and dental caries
- Headache, insomnia, psychosis, mood changes, disorientation, seizures from metabolic imbalance
- Nausea, vomiting, diarrhea, mucositis, weight loss, dry mouth, hiccoughs, constipation
- Well-characterized drug reactions - allergic manifestations, "red man" syndrome, steroid effects
- Well-characterized drug side effects from drugs used routinely in transplant recipients (e.g.; preparative regimen chemotherapy, immunosuppressive drugs, antimicrobials)
- Common side effects of antiemetics, analgesics, anti-inflammatory agent and known complications of steroid therapy

Abbreviated Title: Early BMSC Pilot for Acute GVHD

Version Date: 6/16/2016

- Complications from intravenous catheters, thrombotic occlusion, infection, local reactions, cardiac arrhythmia
- Expected adverse events related to investigational reagents and transplant drugs are listed in section 13.3.

The following are expected transplant outcomes that will be reported in summary form at the time of continuing review but will not be reported to IRB at each occurrence unless they meet the criteria of an SAE or UP:

- Acute graft-versus-host disease
- Chronic graft-versus-host disease
- Graft failure / graft rejection
- Venocclusive disease
- Hemorrhagic cystitis
- Cytomegalovirus reactivation or disease
- Autoimmune phenomena
- EBV reactivation or disease
- Fungal infections
- Disease relapse or progression

